## Purpose of the study

Major depressive disorder (MDD) is highly prevalent and the main cause of global disability worldwide (Kupfer et al., 2012). About 20–40% of patients do not benefit sufficiently from the existing antidepressant interventions, including trials of medication and psychotherapy (Greden, 2001). Pharmacological treatments have limited efficacy, side effects are common (Carvalho et al., 2016), and one-third of patients are medication-resistant failing to achieve remission after using three or more antidepressants (Rush et al., 2006) and experiencing recurrent depressive episodes (Nemeroff, 2007).

For patients with medication-resistant MDD, a number of neuromodulation strategies are available, including electro-convulsive therapy (ECT) and repetitive transcranial magnetic stimulation (rTMS). These are effective interventions, which nonetheless present relatively high costs, may have side-effects and risks (e.g. complications of anesthesia in the case of ECT or risk of seizure induction in the case of rTMS), and require specialized equipment, trained personnel and suitable clinic facilities. This can pose a challenge for some patients as ready access to specialized clinics or treatment centers is not available in all areas of the US or worldwide. The challenge is particularly acute among seniors who have additional limitations in mobility and need help and support to make it to outpatient clinics. And yet, it is estimated that approximately 15% of the elderly (aged > 65) living in the community suffer from clinically significant depressive symptoms (Blazer 2003). Depression in the elderly is a cause of particularly high morbidity and early mortality (Schulz et al. 2002), and older age is a significant predictor of an unfavorable course of depression (Mitchell & Subramanian 2005), reduced likelihood of treatment response (Licht-Strunck et al 2007; Tedeschini et al. 2011), diminished chance of functional recovery (Little et al 1998), and increased risk of relapse (Beekman et al 2002).

At present, given the COVID-19 pandemic and the required and appropriate restrictions on individual mobility and outpatient medical encounters and procedures, access to rTMS, ECT, or similar in-clinic treatments is much more limited. These added difficulties to access ECT and rTMS are occurring at a time when the risk of mental health problems and of decompensation from pre-existing depression is extremely high due to the uncertainties, fears, and stressors caused by the COVID-19 pandemic and the social distancing. The risk of mood and mental health decompensation in the setting of social isolation and loneliness is particularly high among the elderly, who in turn are at a particularly high risk of serious complications of an infection with COVID-19 and thus are faced with particularly high stress, fears, and strict isolation regulations.

Therefore, the current COVID-19 pandemic makes the need for a safe, effective, home-based intervention for an acute, medication-resistant episode of uni- or bi-polar MDD particularly urgent. Transcranial direct current stimulation (tDCS) offers a suitable and readily available solution.

**Study design and purpose:** We propose a safety/feasibility study designed to determine whether it is possible for transcranial direct current stimulation (tDCS) interventions to be successfully delivered by a caregiver at the homes of adults who have medication-resistant MDD.

### **Study objectives:**

**Primary objective:** Demonstrate that remote tDCS sessions applied by a caregiver are feasible, complied and adhered to, and are safe in individuals with severe depression

**Secondary objective:** Gather pilot data on the potential of home-based tDCS to induce clinically meaningful improvements in the severity of depression in individuals who would otherwise be offered rTMS or ECT treatment.

The ultimate goal of this work is to prepare the path for a subsequent randomized clinical trial to assess the antidepressant therapeutic efficacy of home-based tDCS. We thus propose a study of tele-health supervised, caregiver-delivered, home-based tDCS for antidepressant treatment of patients with a medication-resistant depression episode of uni- or bi-polar Major Depression who would otherwise qualify for rTMS or ECT.

Specifically, in the present protocol we seek to offer participation to:

- Patients with medication-resistant MDD who have undergone rTMS or ECT and responded to it but whose benefit has lapsed, and they need repeat a rTMS or ECT course that they cannot access
- Patients with medication-resistant MDD who are undergoing rTMS or ECT and responding, but cannot continue to get the rTMS or ECT course due to COVID-19 pandemic-related regulations or other access concerns
- Patients with medication-resistant MDD who are referred to rTMS or ECT and are found well qualified but cannot access rTMS or ECT due to COVID-19 pandemic-related regulations or other access concerns.

The benefits of this project address a present need due to the COVID-19 pandemic, but also go beyond the present situation and address a larger, pre-existing need.

Across all these potential groups of participants, prospective participants will:

1. Need to have a primary psychiatrist who agrees to their participation in the study and is willing to continue to follow the patient and work collaboratively with the study team
2. Need to be assessed by their primary psychiatrist to be stable enough to be able to remain at home and participate in the present study without undue risk to their safety
3. Need to be living with an adult willing and capable to provide oversight and learn to deliver the home-based tDCS
4. Have the capability to connect with the study team for daily supervision of the intervention sessions and close safety monitoring, and be willing to commit to doing so

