## Benefits

While there are no definitive benefits to participants as a result of participation in this study, MDD participants who received tDCS interventions in prior studies showed improvement of symptoms.

Most recently, Razza et al. (2020) completed a systematic review of all studies of tDCS for treatment of acute major depressive episodes completed up to January 2020. They included all randomized, sham-controlled clinical trials (RCTs) enrolling participants with an acute depressive episode, a total of 23 RCTs with 1,092 participants. They found that active tDCS was superior to sham regarding endpoint depression scores, response and remission rates. Moreover, active tDCS was safe with a side-effect profile comparable to sham.

Moffa et al. (2020) also recently published an individual patient data (IPD) meta-analysis evaluating the efficacy and acceptability of tDCS for treatment of acute major depressive episodes. The IPD meta-analysis is more accurate in estimating the efficacy of an intervention and also superior to the aggregated data approach for obtaining predictors of treatment outcome since it uses the raw data of each participant collected from each study (Riley et al., 2010). Moffa et al. included data from all published placebo-controlled trials on tDCS as only intervention in MDD conducted until December-2018. This included 9 eligible studies with a total of 572 participants. They found active tDCS to be significantly superior to sham for an antidepressant response (30.9% vs. 18.9% respectively; OR = 1.96), remission (19.9% vs. 11.7%, OR = 1.94), and depression improvement (effect size  $\beta = 0.31$ ). Moreover, they found a consistent continuous clinical improvement after the end of the tDCS treatment course. It is noteworthy that the clinical efficacy was substantially higher in the studies where the tDCS course was longer (3-4 weeks versus 1-2 weeks).

The ultimate goal of this work is to identify the potential of tDCS as a home therapy to induce improvements of MDD for patients with the disease. We anticipate that this specific study will demonstrate that remote tDCS sessions are feasible in this population, and offer an important and convenient alternative for multi-session tDCS administration in adults with MDD.

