## Statistical Methods and Analysis

### *Primary*

Feasibility and tolerability/safety will be evaluated using home-based data as it is collected by reported number of aborted sessions.

The *primary outcome* will be change in the observer rated MADRS score from baseline to the 1-month follow-up.

Clinical response is defined as  $\geq 50\%$  improvement in MADRS score from baseline to the 1-month follow-up. Remission is defined as a MADRS score  $\leq 10$ .

The *secondary outcome* measures will include the participant-rated Quick Inventory of Depressive Symptomatology (QIDS-SR) (Rush et al., 2003) and the Quality of Life Enjoyment and Satisfaction Questionnaire Short Form (Q-LES-Q-SF) (Endicott et al., 1993), both administered at the same time points as the MADRS. A computer-based cognitive test battery, CogState (<https://www.cogstate.com>), will provide an additional safety outcome measure. This battery includes tests designed to assess verbal learning and memory (International Shopping List Task), attention and psychomotor function (Detection Task), visual attention (Identification Task), visual learning and memory (One Card Learning Task), working memory (Two Back Task), and executive function (Set Shifting Task).

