## **Statistics**

## **Primary Analysis Plan for efficacy**

The primary outcome measure is the median percentage change (across study subjects) in s MADRS from baseline to 1 month follow up. The significance of changes will be assessed using the non-parametric Wilcoxon signed-rank test; however, since this is a pilot study to determine effect sizes, demonstration of a significant effect is not a defined goal of the study.

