## **Sample Size**

The samples size of 50 is well within the sample size of previous published studies.

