## **Stimulation Stopping criteria**

Subject stimulation will be stopped if any of the following occur during the 8-week treatment period:

- Clinician impression of substantial worsening of medical condition
- If the study subject misses more than 10 stimulation visits.

Study subjects will be withdrawn from the study for the following:

- If the study subject is not compliant with the study procedures as determined by the investigator.
- If, in the investigator's opinion, it is not safe for the study subject to continue with participation in the study.
- If the study subject is withdrawn from the study, the subjects treating psychiatrist will be notified so that arrangements can be made for continued treatment of his/her MDD.
- The study team will be notified by email immediately if the subject reports any adverse events during any tDCS stimulation session, and immediate follow up will occur.
- Any adverse events that take place during testing will be reported to the PI ([name]) and recorded in the database. Drs. [name], [name] and [name] will have primary responsibility for monitoring participant safety in the trial. The investigators will be responsible for reviewing each adverse event in a timely fashion and preparing a summary report for submission to the IRB.

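### The primary objective is to demonstrate feasibility, adherence and safety, but no study-level criterion or precision statement says what result in 50 patients would do so

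*Combined protocol and SAP*

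**What the plan says.** Under Study objectives, the primary objective is to "Demonstrate that remote tDCS sessions applied by a caregiver are feasible, complied and adhered to, and are safe" in people with severe depression. The secondary objective is to gather pilot data on improvement in depression. The same section adds: "The ultimate goal of this work is to prepare the path for a subsequent randomized clinical trial". The Benefits section already expects the answer: "We anticipate that this specific study will demonstrate that remote tDCS sessions are feasible in this population".

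The analysis of that objective is one sentence under Statistical Methods and Analysis, Primary: "Feasibility and tolerability/safety will be evaluated using home-based data as it is collected by reported number of aborted sessions". The same section then says that the primary outcome "will be change in the observer rated MADRS score from baseline to the 1-month follow-up". The only analysis plan that follows concerns efficacy on the MADRS, with the caveat that "demonstration of a significant effect is not a defined goal of the study".

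The Sample Size section reads, in full: "The samples size of 50 is well within the sample size of previous published studies".

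The one adherence number is under Stimulation Stopping criteria, where a subject's stimulation stops "If the study subject misses more than 10 stimulation visits".

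**The concern.** To demonstrate something is to answer a question that could have gone the other way. The study design paragraph under Purpose of the study also poses a yes/no question: whether caregivers can successfully deliver the sessions at home. The plan never says what would amount to no. Half the pairs completing the course and nearly all of them completing it would support the same stated conclusion. A bar chosen after the data are seen cannot repair this.

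The named measure also falls short of the objective. Adherence is part of the objective, but a session never started is not an aborted session. A patient who skips ten sessions and aborts none adds zero to the count.

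The sample size sentence does not say how precisely 50 would estimate an adherence rate or what event rate it could exclude. What is at stake is how the later randomised trial can rely on the primary conclusion.

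**Working it through.** **Can 50 be reproduced?** No. The plan gives no target rate, unacceptable rate, precision, error rate or dropout allowance. The precedent itself is fair. The two meta-analyses described under tDCS and Depression average 1,092/23 = 47.5 and 572/9 = 63.6 participants per trial. The home-based depression reports had 34 participants and one, and the team's own experience is eight pairs. So 50 is an ordinary size, but most of that precedent is sham-controlled efficacy trials, whose size does not show what 50 establishes about caregiver delivery.

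**The rule as written.** With no threshold, success means at least 0 of 50. Its probability is 1.00 whether true adherence is 30%, 70% or 90%.

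**What 50 can show.** For x of n, the exact (Clopper-Pearson) 95% limits are the 0.025 quantile of Beta(x, n−x+1) and the 0.975 quantile of Beta(x+1, n−x).

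| Completing | Exact 95% interval |
|---|---|
| 35/50 | 55.4% to 82.1% |
| 40/50 | 66.3% to 90.0% |
| 45/50 | 78.2% to 96.7% |

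**An illustrative bar.** Suppose feasibility is concluded only if the lower two-sided limit exceeds a bar p0. This is the same as requiring x large enough that P(X ≥ x | p0) < 0.025. For p0 = 70%, 41/50 gives a lower limit of 68.6% (fails) and 42/50 gives 70.9% (passes). With X ~ Binomial(50, p), P(X ≥ 42) is 0.942 at p = 0.90, 0.668 at p = 0.85 and 0.018 at p = 0.70.

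The documents give no bar, so here is the range:

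| Bar (assumed) | Needed of 50 | Chance of passing |
|---|---|---|
| 60% | 38 | 81% at a true 80% |
| 70% | 42 | 94% at 90%; 67% at 85% |
| 75% | 44 | 77% at 90% |
| 80% | 46 | 43% at 90%; 90% at 95% |

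With a one-sided 5% limit instead, the 70% bar needs 41/50, and the chance of passing is 98% at 90% and 79% at 85%.

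**Safety.** If no serious event is seen, the upper limit is 1 − 0.025^(1/50) = 7.1% (two-sided) or 1 − 0.05^(1/50) = 5.8% (one-sided). A true 2% event rate would produce at least one event with probability 1 − 0.98^50 = 0.64, so seeing none is quite compatible with it.

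**The missed-visit limit.** There are 28 daily and 9 taper sessions, 37 in all. Missing 10 leaves 27, and 27/37 = 73%. This is not an exact complement of the stopping rule, which counts missed visits. The session rules treat an aborted session separately: it uses up its slot, and in the taper it counts among those administered. A patient with 8 missed and 5 aborted sessions stays within the limit but has completed 37 − 13 = 24.

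**The case against.** This is a pilot, and a pilot needs no power calculation. That is right, and none is asked for; the gap is a criterion and a precision statement. The plan's disclaimer about significance sits in the efficacy section and concerns the MADRS test, so it does not cover the objective to demonstrate feasibility.

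It may be said that the plan does contain a bar, the limit on missed visits. That rule stops one person's stimulation. It does not say how many people may reach it before home delivery is judged not feasible.

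The session rules say that adherence will be monitored through completed sessions, and staff are notified of sessions not completed within the agreed window. So the data will exist. But the statistical section does not use them.

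An estimated completion rate with its interval helps plan a trial even without a pass mark. This stands: a reader might infer that the study would carry no information, and that goes too far.

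The listed annexes and forms were not available, so a criterion there cannot be excluded. Neither the objectives nor the statistical sections refer to one.

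**Conclusion.** The point holds as a missing study-level success criterion and a missing precision statement for the primary objective. It rests on the text alone. Every bar and true rate used above is an assumption, there to show that 50 could carry a criterion.

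Three stronger readings are not supported:

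- **That 50 is too small, or out of line with earlier work.** It is close to the average size of the cited trials and adequate for several plausible bars, though not for separating 80% from 90%, where the chance of passing is 43%.
- **That 50 might mean 25 patients, because caregivers are also called participants.** The sample size follows directly on an outcome taken across study subjects, only patients have a MADRS outcome, and the withdrawal and stopping sections use study subject for the person stimulated. A clarifying word is enough.
- **That the protocol promises a formal go/no-go decision.** It speaks only of preparing for a randomised trial; what can be said is that no progression criterion is stated.

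The study can run without the change, but its primary conclusion would be reached whatever the data showed.

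**What to change.** **Sample Size.** State that 50 means 50 patients, each with a caregiver, and give the precision this provides, for example 78% to 97% if 45 of 50 complete.

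**Statistical Methods and Analysis, Primary.** Keep the aborted-session count and add:

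- Feasibility is the proportion of enrolled pairs completing at least a stated number of the 37 scheduled sessions. Using 27 of 37 is one option, informed by the missed-visit limit but not identical to it. This is an analysis definition and leaves the stopping rule untouched.
- Aborted sessions do not count as completed.
- Feasibility is concluded only if the lower exact two-sided 95% limit exceeds a bar fixed before enrolment. The sponsor chooses the bar; 70% would need 42 of 50.
- Safety is reported as the serious-event rate with its exact upper limit (7.1% two-sided or 5.8% one-sided if none occur in 50), not as a bare statement that the treatment is safe.

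Amend both sections together, so that the plan does not hold two unreconciled feasibility measures.

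**Cost.** Protocol wording only. Session completion is already monitored, and no extra patients are needed. The downside is that the study can then miss its primary objective.

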### Exclusion criteria for Participant caregiver-administrators:

- Poor eyesight,
- Severe arthritis in the hands, pain, deformity or other condition that interferes with successful administration of tDCS.
- Inability to understand study procedures following review of the Informed Consent form.

Understanding will be assessed by asking the participant caregiver-administrator to answer the following three questions:

- 1) What is the purpose of this study?
- 2) What are the risks of study involvement?
- 3) If you decide to participate, are you allowed to withdraw from the study at any time?

Answers will be recorded by study personnel on the "Assessment of Protocol Understanding" form (see attached). Insufficient understanding will be defined by one or more incorrect answers, as determined at the discretion of the investigator

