### Visits (All visits will be conducted remotely)

For this study, participant caregiver administrators will be provided remote step-by-step training to administer the tDCS sessions to the participants with MDD. Participant caregiver-administrators will be directly supervised remotely, until they demonstrate proficiency, without coaching by the study team. We have developed a step by step training manual, and have successfully trained older adult caregivers to administer the tDCS.

Visit	Purpose	Procedures	Study personnel	Duration	Location
Pre-ICF	Advance review	Informed consent pre-review by potential participants	RA will send	As needed for review	Mailed/emailed to P
Visit 1	Remote screen and assessment visit	Informed consent [ P with MDD ] Mental Health/Medical health history; medications; Cognitive Assessment; Interview with study psychiatrist [ Participant caregiver-administrators ] Health history; computer proficiency questionnaire [ Both participants ] tDCS overview and training	Study research assistant; Study psychiatrist	~ 1 hour	Remote
Home tDCS administration Treatment period – Daily tDCS sessions over 4 weeks *Participant ratings of suicidality will be completed each day, and responses will be monitored and immediately be reviewed in real time by the study RA and study psychiatrist. Any changes from baseline will result in an immediate contact to the participant by the study psychiatrist.					
Week (Wk)1; Day (D) 1	Home-based tDCS	At-home tDCS equipment set-up; tDCS administration by caregiver-administrator with step-by- step remote training by study staff Daily diary	Study research assistant	1 hour total (tDCS session=30 mins)	Video conference
Wk1, tDCS session	Home-based tDCS once a day	tDCS admin by the caregiver-administrator with remote staff oversight and coaching Daily	Study research assistant	1 hour total (tDCS session=30)	Video conference

D 2-4		diary		mins)	
Wk 1, tDCS session D 5	Home-based tDCS	tDCS admin by the caregiver-administrator with remote staff oversight and coaching; Staff administered skills test for caregiver-administrators Daily diary	Study research assistant	1 hour total (tDCS session=30 mins)	Video conference
Wk 1-4; D6-28	Home-based tDCS once a day	The caregiver-administrator will administer the in-home tDCS session with remote staff monitoring and video conferencing if necessary Daily diary	Study research assistant	1 hour	Participant's Home

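### Feasibility is counted only from sessions that start, in pairs selected for likely success, so consented pairs that cannot be trained or never start leave no failure on record

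*Combined protocol and SAP*

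**What the plan says.** **The question.** Under Purpose of the study, the protocol asks whether tDCS can be "successfully delivered by a caregiver at the homes of adults who have medication-resistant MDD". The primary objective, under Study objectives, is: "Demonstrate that remote tDCS sessions applied by a caregiver are feasible, complied and adhered to, and are safe in individuals with severe depression".

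**Who may enter.** Study objectives, repeated under Eligibility Criteria, sets two relevant conditions for every participant. The first is "Need to be living with an adult willing and capable to provide oversight and learn to deliver the home-based tDCS". The second is the ability and commitment to connect with the team for daily supervision. The inclusion criteria add age 50 or older and a willing and able caregiver. Caregivers must report comfort with computers and state that they are available throughout. They are excluded for poor eyesight, or for "Severe arthritis in the hands, pain, deformity or other condition that interferes with successful administration of tDCS".

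**When training happens.** Consent is taken at the start of the screening call (Process of Consent). Visit 1, a screening and assessment visit, lists consent first and also lists "tDCS overview and training". Equipment set-up and coached administration run from Day 1, and a staff-administered skills test falls on Day 5. Both lie inside the treatment period.

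**What is measured.** Statistical Methods and Analysis, Primary, says: "Feasibility and tolerability/safety will be evaluated using home-based data as it is collected by reported number of aborted sessions". It gives no denominator, point of enrolment or success threshold. No section plans a count of pairs screened, excluded and lost.

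**What is expected.** Benefits says: "We anticipate that this specific study will demonstrate that remote tDCS sessions are feasible in this population".

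**The concern.** Two things combine. The entry criteria favour pairs likely to manage home delivery, which is sensible for safety but narrows the group to which a result applies. The measure then looks only at sessions already under way. A consented pair that stalls before its first session is a feasibility failure in any ordinary sense, yet the measure does not register it.

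This matters because feasibility is the primary objective and the stated purpose is to prepare a randomised trial. That trial needs to know how many consented pairs reach treatment, and how many patients must be screened to find them. The device and training section itself reports that, in an earlier home study, the procedure kept some caregivers from reaching competency. It also says that the team's own eight pairs were trained in person. Whether caregivers can be trained by video is thus one of the main new questions here, and it is where failures could go uncounted.

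**Working it through.** **No feasibility figure to reproduce.** The sample size of 50 is supported only by comparison with earlier studies. No rate, precision, alpha or power is given.

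**Step 1: what the measure can see.** Planned sessions are 28 daily + 9 taper = 37. A pair that completes all 37 has 0 aborted sessions. A pair that consents and never starts also has 0. A pair that aborts its first session and stops has 1, the same as a pair that aborts one and completes 36. The count cannot separate these outcomes. The device also reports sessions not completed within their window, so relevant data exist, but the stated measure does not use them.

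**Step 2: effect of leaving out consented pairs.** Assume 45 of 50 pairs that start are successes. Let k be the number of further eligible consented pairs lost before Day 1. The proper rate is 45/(50 + k), with exact (Clopper-Pearson) 95% intervals:

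| k (assumed) | Rate | 95% CI |
|---|---|---|
| 0 | 45/50 = 90% | 78-97% |
| 2 | 45/52 = 87% | 74-94% |
| 5 | 45/55 = 82% | 69-91% |
| 10 | 45/60 = 75% | 62-85% |

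Both the 45 and k are assumptions. With k = 0 there is no overstatement.

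**Step 3: reading the result beyond eligible pairs.** Let s be the share of the wider population that passes entry, f feasibility among those who enter, and g feasibility among those who do not. Wider feasibility is s×f + (1 − s)×g. With f = 0.90:

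| s (assumed) | g = 0 | g = 0.5 |
|---|---|---|
| 0.9 | 0.81 | 0.86 |
| 0.7 | 0.63 | 0.78 |
| 0.5 | 0.45 | 0.70 |
| 0.3 | 0.27 | 0.62 |

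For example, at s = 0.7 and g = 0.5: 0.7×0.90 + 0.3×0.5 = 0.78. The result falls below 0.90 whenever g < f and s < 1, but the documents give neither s nor g. The sampling interval around 45/50 does not cover this uncertainty.

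**Step 4: screening yield.** Enrolling 50 pairs needs about 50/s screened: 50/0.7 = 72 (rounded up) or 50/0.5 = 100. The later trial needs s, and the plan does not collect it as a result.

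**The case against.** The strongest case against runs as follows. The criteria are predictors of success, not success itself. Computer comfort and availability are self-reported. Hands-on coaching, the skills test, missed sessions and the rule on more than 10 missed visits all come after entry, so a pair can meet every criterion and still fail on record. The question is already limited to caregiver delivery, and the restrictions are stated openly, so a patient without a caregiver lies outside it. The broad conclusion is one anticipatory sentence under Benefits, not an analysis statement.

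All of that stands. It rules out three stronger readings that a reader might infer:

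- *The feasibility result is conditioned on its own outcome.* It is not: failure remains observable after entry.
- *Training at Visit 1 is a run-in that removes failures.* No section makes passing training an entry rule or says that a failing caregiver becomes ineligible. Visit 1 lasts about an hour, covers many other items and lists no caregiver administration. In context, the exclusion for an interfering condition most naturally means physical impairment.
- *Every excluded patient is a hidden delivery failure.* That assumes g = 0, which the documents do not support, and it merges access to a caregiver with deliverability.

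The objection does not answer the denominator gap. Following the stated measure exactly, a consented eligible pair that never starts contributes nothing.

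**Conclusion.** The concern holds in a limited form. The feasibility measure has no denominator and cannot register eligible, consented pairs that fail before a session starts. If such pairs exist, delivery looks more feasible than it was. Separately, the result describes patients aged 50 or older with an eligible caregiver, not adults with medication-resistant depression in general. It also says little about older people living alone, although the rationale stresses social isolation among the elderly. That second part is a limit on generalisability, not a bias within eligible pairs.

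The size is unknown. The fall from 90% to 82% rests on an assumed 45 successes and 5 uncounted pairs, and it is zero if no consented pair is lost. The direction in the wider population rests on excluded patients doing worse than enrolled ones, which is plausible but not documented.

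**What to change.** Change Statistical Methods and Analysis, Primary, as follows:

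1. **Denominator.** Use all eligible pairs that consent. Because consent, screening and the training overview share Visit 1, record eligibility and fix the denominator before any training begins.
2. **Failures.** Count pairs that fail training, fail the Day 5 skills test or never start a session as feasibility failures. State that they may not be reclassified as ineligible under the caregiver exclusions. Because caregivers are supervised until proficient, define in advance what counts as failing training.
3. **Sessions.** Report completed, missed and aborted sessions out of the 37 planned.
4. **Screening table.** List pairs screened out before enrolment separately by reason: no capable adult in the home, connection, computer comfort, availability, or physical condition. Do not score them as delivery failures.
5. **Conclusion.** State it for patients aged 50 or older with an eligible caregiver, and align the sentence under Benefits.

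To make the reasons in item 4 unambiguous, reconcile the live-in requirement under Study objectives with the inclusion criteria, which allow a friend as caregiver without repeating it.

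The cost is a few sentences and one extra table. Phone-screen questionnaires for both members and a caregiver competency checklist are already on the list of forms, and no patients or visits are added. No entry or safety screen is relaxed. The downside is a possibly less favourable feasibility figure.
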